## 2.4 Prognosis and Treatment

While most NETs are relatively slow-growing (G1 or G2) with a median survival of many years, the prognosis of patients with poorly differentiated G3 NECs is dismal with a median

survival of approximately 12 months (2). Common sites of metastases include liver, lung, bones, and brain. Histologically, poorly differentiated NECs can be classified as either “small cell” or “large cell” NEC. Clinically these entities behave very similarly and standard treatment for both large and small cell NEC is usually identical, although some practitioners favor temozolomide-based chemotherapy regimens over platinum-based regimens in patients with poorly differentiated NEC with Ki-67 <55% (2).

As this is a relatively rare patient population, large-scale, randomized phase III trials have been very difficult to perform. Standard accepted therapies have been extrapolated from experience in the treatment of SCLC or are based on smaller phase II trials in this specific population. First-line treatment generally involves chemotherapy, either platinum-based (e.g. carboplatin or cisplatin in combination with etoposide) or temozolomide-based (e.g. single-agent temozolomide, capecitabine + temozolomide). Response rates range from 10 – 70% but are generally not durable with no standard second-line treatment (2-4). Extrapolating from treatment algorithms used in small cell lung cancer (SCLC), chemotherapy is often administered in the second-line setting with disappointingly low response rates and early clinical progression (5-7).

### **3 DRUG INFORMATION**

#### **3.1 Pembrolizumab**

Refer to the Investigator’s Brochure (IB) for detailed background information on MK-3475 (Pembrolizumab).

##### **3.1.1 Pharmaceutical and Therapeutic Background**

The importance of intact immune surveillance in controlling outgrowth of neoplastic transformation has been known for decades. Accumulating evidence shows a correlation between tumor-infiltrating lymphocytes (TILs) in cancer tissue and favorable prognosis in various malignancies. In particular, the presence of CD8+ T-cells and the ratio of CD8+ effector T-cells / FoxP3+ regulatory T-cells seems to correlate with improved prognosis and long-term survival in many solid tumors.

The PD-1 receptor-ligand interaction is a major pathway hijacked by tumors to suppress immune control. The normal function of PD-1, expressed on the cell surface of activated T-cells under healthy conditions, is to down-modulate unwanted or excessive immune responses, including autoimmune reactions. PD-1 (encoded by the gene Pdcd1) is an Ig superfamily member related to CD28 and CTLA-4 which has been shown to negatively regulate antigen receptor signaling upon engagement of its ligands (PD-L1 and/or PD-L2). The structure of murine PD-1 has been resolved. PD-1 and family members are type I transmembrane glycoproteins containing an Ig Variable-type (V-type) domain responsible for ligand binding and a cytoplasmic tail which is responsible for the binding of signaling molecules. The cytoplasmic tail of PD-1 contains 2 tyrosine-based signaling motifs, an immunoreceptor tyrosine-based inhibition motif (ITIM) and an immunoreceptor tyrosine-based switch motif (ITSM). Following T-cell stimulation, PD-1 recruits the tyrosine phosphatases SHP-1 and SHP-2 to the ITSM motif within its cytoplasmic tail, leading to the dephosphorylation of effector molecules such as CD3 $\zeta$ , PKC $\theta$  and ZAP70 which are involved in the CD3 T-cell signaling cascade. The mechanism by which PD-1 down modulates T-cell responses is similar

to, but distinct from that of CTLA-4 as both molecules regulate an overlapping set of signaling proteins. PD-1 was shown to be expressed on activated lymphocytes including peripheral CD4+ and CD8+ T-cells, B-cells, Tregs and Natural Killer cells. Expression has also been shown during thymic development on CD4-CD8- (double negative) T-cells as well as subsets of macrophages and dendritic cells. The ligands for PD-1 (PD-L1 and PD-L2) are constitutively expressed or can be induced in a variety of cell types, including non-hematopoietic tissues as well as in various tumors. Both ligands are type I transmembrane receptors containing both IgV- and IgC-like domains in the extracellular region and contain short cytoplasmic regions with no known signaling motifs. Binding of either PD-1 ligand to PD-1 inhibits T-cell activation triggered through the T-cell receptor. PD-L1 is expressed at low levels on various non-hematopoietic tissues, most notably on vascular endothelium, whereas PD-L2 protein is only detectably expressed on antigen-presenting cells found in lymphoid tissue or chronic inflammatory environments. PD-L2 is thought to control immune T-cell activation in lymphoid organs, whereas PD-L1 serves to dampen unwarranted T-cell function in peripheral tissues. Although healthy organs express little (if any) PD-L1, a variety of cancers were demonstrated to express abundant levels of this T-cell inhibitor. PD-1 has been suggested to regulate tumor-specific T-cell expansion in subjects with melanoma (MEL). This suggests that the PD-1/PD-L1 pathway plays a critical role in tumor immune evasion and should be considered as an attractive target for therapeutic intervention.

Pembrolizumab is a potent and highly selective humanized monoclonal antibody (mAb) of the IgG4/kappa isotype designed to directly block the interaction between PD-1 and its ligands, PD-L1 and PD-L2. Keytruda™ (pembrolizumab) has recently been approved in the United States for the treatment of patients with unresectable or metastatic melanoma and disease progression following ipilimumab and, if BRAF V600 mutation positive, a BRAF inhibitor.

### **3.1.2 Preclinical and Clinical Trial Data**

Refer to the Investigator's Brochure for Preclinical and Clinical data.

## **3.2 Rationale for the Trial and Selected Subject Population**

### **3.2.1 Rationale for anti-PD-1 therapy in high grade (G3) NET/NECs**

Immunotherapy, in particular therapy with immune checkpoint inhibitors such as anti-PD-1 antibody therapy, has recently shown significant efficacy in a wide variety of tumors with FDA approved indications for anti-PD-1 antibody therapy includes melanoma, non-small cell lung cancer, squamous cell carcinoma of the head and neck, renal cell cancer, and Hodgkin lymphoma. Additionally, phase II trials have demonstrated activity in other cancer types including small cell lung (SCLC), merkel cell, bladder, gastric, hepatobiliary, breast and prostate cancers. Included in this list of cancers where activity has been demonstrated are two aggressive neuroendocrine cancers: Merkel cell carcinoma and small cell lung cancer.

The multicenter, phase 2 clinical trial leading to wide acceptance of pembrolizumab therapy in patients with advanced Merkel cell carcinoma demonstrated an objective response rate of 56% with a response duration ranging from 2.2 months to at least 9.7 months and a 6-month progression-free survival rate of 67% (9). Similarly, trials demonstrating activity of anti-PD-1 antibody therapy in SCLC include the KEYNOTE-028 trial and the CHECKMATE-032 trial. In the KEYNOTE-028 trial, patients with metastatic SCLC with evidence of PD-L1

expression by immunohistochemistry who were previously treated with platinum-based chemotherapy were treated with pembrolizumab. Early data suggest a 25% response rate with response duration lasting > 4 months (10). The CHECKMATE-032 trial enrolled a similar patient population. Patients were treated with nivolumab either alone or in combination with ipilimumab with response rates of 13% and 31% respectively and duration of responses lasting > 6 months (11). With this encouraging data, multiple ongoing trials are evaluating the role of anti-PD-1 therapy and other immune checkpoint inhibitors in the treatment of patients with Merkel cell carcinoma and SCLC. These trials all support the rationale for treatment with immune checkpoint blockade in patients with high grade NET/NECs.

Among biologic correlates evaluated with anti-PD-1 therapies, none have defined a clear subset to definitively predict clinical efficacy. However, some correlates have emerged as strong predictors for clinical benefit. Three leading correlative markers predictive of benefit include: 1) mutation burden (namely, cancers with higher mutation burden tend to be more likely to respond to anti-PD-1 therapy, likely due to an increase in neoantigen expression) (12); 2) PD-L1 expression (13-14); and, 3) tumor T cell infiltration, associated with PD-L1 expression by infiltrating immune cells (15-16). High grade NECs have been shown to have a high mutation burden (17-18). Similarly, NECs have been found to express PD-L1, which is more commonly expressed in G3 NECs (19). Lastly, the majority of extra-pulmonary higher grade NETs have also been shown to exhibit intratumoral T cell infiltration on histopathologic review (20). Together, these features suggests a higher likelihood of clinical benefit in this patient population.

### **3.2.2 Rationale for Dose Selection/Regimen/Modification**

An open-label Phase I trial (Protocol 001) is being conducted to evaluate the safety and clinical activity of single agent MK-3475. The dose escalation portion of this trial evaluated three dose levels, 1 mg/kg, 3 mg/kg, and 10 mg/kg, administered every 2 weeks (Q2W) in subjects with advanced solid tumors. All three dose levels were well tolerated and no dose-limiting toxicities were observed. This first in human study of MK-3475 showed evidence of target engagement and objective evidence of tumor size reduction at all dose levels (1 mg/kg, 3 mg/kg and 10 mg/kg Q2W). No MTD has been identified to date. 10.0 mg/kg Q2W, the highest dose tested in PN001, will be the dose and schedule utilized in Cohorts A, B, C and D of this protocol to test for initial tumor activity. Recent data from other clinical studies within the MK-3475 program has shown that a lower dose of MK-3475 and a less frequent schedule may be sufficient for target engagement and clinical activity.

PK data analysis of MK-3475 administered Q2W and Q3W showed slow systemic clearance, limited volume of distribution, and a long half-life (refer to IB). Pharmacodynamic data (IL-2 release assay) suggested that peripheral target engagement is durable (>21 days). This early PK and pharmacodynamic data provides scientific rationale for testing a Q2W and Q3W dosing schedule.

A population pharmacokinetic analysis has been performed using serum concentration time data from 476 patients. Within the resulting population PK model, clearance and volume parameters of MK-3475 were found to be dependent on body weight. The relationship between clearance and body weight, with an allometric exponent of 0.59, is within the range observed for other antibodies and would support both body weight normalized dosing or a

fixed dose across all body weights. MK-3475 has been found to have a wide therapeutic range based on the melanoma indication. The differences in exposure for a 200 mg fixed dose regimen relative to a 2 mg/kg Q3W body weight based regimen are anticipated to remain well within the established exposure margins of 0.5 – 5.0 for MK-3475 in the melanoma indication. The exposure margins are based on the notion of similar efficacy and safety in melanoma at 10 mg/kg Q3W vs. the proposed dose regimen of 2 mg/kg Q3W (i.e. 5-fold higher dose and exposure). The population PK evaluation revealed that there was no significant impact of tumor burden on exposure. In addition, exposure was similar between the NSCLC and melanoma indications. Therefore, there are no anticipated changes in exposure between different indication settings.

The rationale for further exploration of 2 mg/kg and comparable doses of pembrolizumab in solid tumors is based on: 1) similar efficacy and safety of pembrolizumab when dosed at either 2 mg/kg or 10 mg/kg Q3W in melanoma patients, 2) the flat exposure-response relationships of pembrolizumab for both efficacy and safety in the dose ranges of 2 mg/kg Q3W to 10 mg/kg Q3W, 3) the lack of effect of tumor burden or indication on distribution behavior of pembrolizumab (as assessed by the population PK model) and 4) the assumption that the dynamics of pembrolizumab target engagement will not vary meaningfully with tumor type.

The choice of the 200 mg Q3W as an appropriate dose for the switch to fixed dosing is based on simulations performed using the population PK model of pembrolizumab showing that the fixed dose of 200 mg every 3 weeks will provide exposures that 1) are optimally consistent with those obtained with the 2 mg/kg dose every 3 weeks, 2) will maintain individual patient exposures in the exposure range established in melanoma as associated with maximal efficacy response and 3) will maintain individual patients exposure in the exposure range established in melanoma that are well tolerated and safe.

A fixed dose regimen will simplify the dosing regimen to be more convenient for physicians and to reduce potential for dosing errors. A fixed dosing scheme will also reduce complexity in the logistical chain at treatment facilities and reduce wastage.

## **4 STUDY DESIGN**

### **4.1 Description**

This is an open label, non-randomized phase 2 study to assess overall response rate (ORR), clinical benefit rate (CBR), overall survival (OS) and progression free survival (PFS) in patients with high grade neuroendocrine tumors treated with pembrolizumab 200mg Q 3 Weeks.

Simon Optimum Two-Stage designs will be used. A Type I error rate alpha equal to 0.10 and a Type II error rate beta equal to 0.20 will be used. Null and alternative hypotheses are associated with treatments. See Section 12 for additional details

### **4.2 Number of Patients**

A total of 34-40 subjects will be recruited to one treatment arm in this study with the goal of enrolling 34 evaluable patients (defined in sections 11.1 and 11.3).

#### **4.3 Number of Study Centers**

This trial will open as a multi-site study conducted at the Huntsman Cancer Institute including various other satellite sites and Intermountain Healthcare.

#### **4.4 Study Duration**

We would anticipate that on average, patients will remain on treatment approximately 24 weeks (range of 2 to 52 weeks comparatively). However, patients may remain on treatment pembrolizumab for up to 2 years as long as they are receiving clinical benefit (SD, PR, CR), or until irRECIST progressive disease (PD) is confirmed. Confirmation of progression will occur 4-6 weeks after first detection prior to subject coming off study.

Accrual is anticipated to take 24-30 months. Estimated duration of accrual and patient participation is approximately three and half years.

## 5 ELIGIBILITY CRITERIA

This eligibility checklist is used to determine patient eligibility and filed with signature in the patient research chart.

**Patient No.** \_\_\_\_\_

**Patient's Initials: (L,F,M)** \_\_\_\_\_

### 5.1 Inclusion Criteria

**Yes/No (Response of "no" = patient ineligible)**

**5.1.1** \_\_\_\_\_ Histologically confirmed, metastatic or unresectable neuroendocrine carcinoma of non-pulmonary origin, high grade as indicated by Ki-67 >20% and/or > 20 mitoses/10 hpf. Patients must have existing Ki-67 results from archival tissue or available tissue for Ki-67 testing. If no archival tissue is available the subject must agree to a fresh biopsy for testing to qualify for the study.

**5.1.2** \_\_\_\_\_ Patients must have progressed during or after first-line treatment for metastatic or unresectable disease with either a platinum-based regimen (e.g. carboplatin + VP16, cisplatin + VP-16, FOLFOX) OR temozolomide-based regimen. Patients must have failed at least one line of therapy but no maximum number of therapies is exclusionary (i.e. second-line therapy and beyond).

**5.1.3** \_\_\_\_\_ Have measurable disease based on irRECIST.

**5.1.4** \_\_\_\_\_ Be  $\geq$  18 years of age on day of signing informed consent.

**5.1.5** \_\_\_\_\_ Have a performance status of 0 or 1 on the ECOG Performance Scale.

**5.1.6** \_\_\_\_\_ Demonstrate adequate organ function as defined in Table 2, all screening labs should be performed within 14 days of treatment initiation.

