### 2.2 Neuroendocrine carcinoma (NECs) / Neuroendocrine Tumors (NETs)

Neuroendocrine tumors (NETs) make up a relatively rare but heterogeneous family of neoplasms. Historically considered rare, the incidence of NETs has been steadily increasing since the 1970s, with SEER registry data suggesting an increase in incidence of almost 500% over this period of time in the United States (1). These tumors arise from neuroendocrine cells that are found primarily in the gut and make up the largest group of hormone-producing cells in the body. The hallmark of NETs is evidence of predominant neuroendocrine differentiation; namely, they have distinctive morphologic characteristics and expression of specific tissue markers including chromogranin A, synaptophysin, and neuron-specific enolase. These tumors commonly arise in the lung, intestine and pancreas but can arise in various anatomic locations including the larynx, thymus, kidneys, cervix, prostate, ovaries, and other sites. No primary site is identified in approximately 10 – 15% of metastatic NET cases (1).

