## 2.3 NET / NEC Classification and Grading

The pathologic classification of non-pulmonary neuroendocrine malignancies is complex and continually evolving. Low grade, well-differentiated neuroendocrine neoplasms are commonly referred to as “neuroendocrine tumors” (NETs) whereas high grade, poorly differentiated neuroendocrine neoplasms are commonly referred to as “neuroendocrine carcinoma” (NECs). Pathologic specimens are distinguished based on morphologic evidence of differentiation. Well-differentiated NETs show a solid, trabecular, gyriform, or glandular pattern with uniform nuclei, salt-and-pepper chromatin, and finely granular cytoplasm. Poorly differentiated NECs resemble small cell or large cell neuroendocrine carcinoma of the lung. Small cell NECs are comprised of small round cells with small amounts of cytoplasm with hyperchromatic nuclei; large cell NEC cells are arranged in organoid, trabecular, or palisading patterns with prominent necrosis.

The 2010 WHO classifications of gastroenteropancreatic neuroendocrine tumors (GEP-NETs) adopted a classification system previously endorsed by the European Neuroendocrine Tumour Society (ENETS). Namely, well-differentiated tumors are separated into low-grade and intermediate-grade with poorly-differentiated tumors generally classified as high grade depending on mitotic count and/or Ki-67 proliferation indices (Table 1). The WHO Grade 3 (G3) of NECs is somewhat heterogenous. Namely, the majority of NECs exhibit a poorly differentiated morphology and will fall in the range of G3 tumors based on mitotic or proliferative indices; however, a subset of patients will exhibit a well- or moderately-differentiated histology but higher grade based on mitotic and proliferative indices. These tumors are considered “grade discordant.” Their clinical behavior generally falls somewhere between lower grade NETs and poorly differentiated, G3 NECs.

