**5.2.8**  Has known active central nervous system (CNS) metastases and/or carcinomatous meningitis. Subjects with previously treated brain metastases may participate provided they are stable (without evidence of progression by imaging for at least 2 weeks prior to the first dose of trial treatment and any neurologic symptoms have returned to baseline), have no evidence of new or enlarging brain metastases, and are not using steroids for at least 7 days prior to trial treatment. This exception does not include carcinomatous meningitis which is excluded regardless of clinical stability.

**5.2.9**  Has active autoimmune disease that has required systemic treatment in the past 2 years (i.e. with use of disease modifying agents, Replacement therapy (e.g. thyroxine, insulin, or physiologic corticosteroid replacement therapy for adrenal or pituitary insufficiency, etc.) is not considered a form of systemic treatment.

**5.2.10**  Has known history of (non-infectious) pneumonitis that required steroids or has current pneumonitis.

**5.2.11**  Has an active infection requiring systemic therapy.

**5.2.12**  Has a history or current evidence of any condition, therapy, or laboratory abnormality that might confound the results of the trial, interfere with the subject's participation for the full duration of the trial, or is not in the best interest of the subject to participate, in the opinion of the treating investigator.

**5.2.13**  Has known psychiatric or substance abuse disorders that would interfere with cooperation with the requirements of the trial.

**5.2.14**  Is pregnant or breastfeeding, or expecting to conceive or father children within the projected duration of the trial, starting with the pre-screening or screening visit through 120 days after the last dose of trial treatment.

**5.2.15**  Has received prior therapy with an anti-PD-1, anti-PD-L1, or anti-PD-L2 agent.

**5.2.16**  Has a known history of Human Immunodeficiency Virus (HIV) (HIV 1/2 antibodies).

**5.2.17**  Has known active Hepatitis B (e.g., HBsAg reactive) or Hepatitis C (e.g., HCV RNA [qualitative] is detected).

**5.2.18**  Has received a live vaccine within 30 days of planned start of study therapy.  
Note: Seasonal influenza vaccines for injection are generally inactivated flu vaccines and are allowed; however intranasal influenza vaccines (e.g., Flu-Mist®) are live attenuated vaccines, and are not allowed.

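### Does the silence of 5.1.1 on Merkel cell carcinoma endanger the primary response rate?

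*Combined protocol and SAP*

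**What the plan says.** Criterion 5.1.1 requires "Histologically confirmed, metastatic or unresectable neuroendocrine carcinoma of non-pulmonary origin", with Ki-67 above 20% and/or more than 20 mitoses per 10 high-power fields. The study summary and the primary objective (1.1) also limit site only by the term non-pulmonary. None of 5.2.1 to 5.2.18 mentions Merkel cell carcinoma or skin primaries.

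The background bears on the question without deciding it:

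- Section 2.2 says these tumours "can arise in various anatomic locations including the larynx, thymus, kidneys, cervix, prostate, ovaries, and other sites". Skin is not named, but the list is open.
- Section 2.3 states that "Poorly differentiated NECs resemble small cell or large cell neuroendocrine carcinoma of the lung", and 2.4 adds that "poorly differentiated NECs can be classified as either" small cell or large cell.
- Section 3.2.1 lists Merkel among further cancer types with phase 2 activity, then refers to "two aggressive neuroendocrine cancers: Merkel cell carcinoma and small cell lung cancer" as tumours where activity has been shown. It describes the Merkel trial as "leading to wide acceptance of pembrolizumab therapy in patients with advanced Merkel cell carcinoma demonstrated an objective response rate of 56" percent.

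Three criteria narrow entry. Under 5.1.2, "Patients must have progressed during or after first-line treatment for metastatic or unresectable disease with either a platinum-based regimen" or a temozolomide-based one. Criterion 5.2.15 excludes prior anti-PD-1, anti-PD-L1 or anti-PD-L2 therapy. Criterion 5.2.12 lets the treating investigator exclude a patient with any condition that "might confound the results of the trial".

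Section 6 states that there is one arm and no stratification. Section 12 tests one pooled response rate and plans no analysis by primary site.

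**The concern.** Section 3.2.1 borrows support from two tumours. The non-pulmonary limit removes one of them, small cell lung cancer, and nothing in Section 5 expressly removes the other. Merkel comes with a cited response rate of 56%, against a null of 10% and an alternative of 25%. The final cutoff is 6 responses in 34, so one responder can decide the trial.

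If a Merkel patient enrolled and responded, a result just past the cutoff might be read as activity across the rest of high-grade neuroendocrine carcinoma when part of it came from a tumour already known to respond. Registration is checked against Section 5 (Section 13) and the trial is multi-site (4.3), so two sites could in principle answer the eligibility question differently.

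**Working it through.** **Inputs.** From Section 12: null 10%, alternative 25%, alpha 0.10, beta 0.20, continue if at least 2 of 13 respond, reject the null if at least 6 of 34 respond. From 3.2.1: Merkel response rate 56%. Assumed, because the documents give no figure: the number k of Merkel patients among the 34 (0, 1 or 2), and a lower Merkel rate of 25%, since the 56% is cited for advanced disease and not shown to hold after platinum.

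**Step 1: reproduce the design.** With X₁ ~ Bin(13, p) and X₂ ~ Bin(21, p), P(reject) = Σ over x ≥ 2 of P(X₁ = x) · P(X₂ ≥ 6 − x). At p = 0.10:

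| x | P(X₁ = x) | P(X₂ ≥ 6 − x) | product |
|---|---|---|---|
| 2 | 0.2448 | 0.1520 | 0.0372 |
| 3 | 0.0997 | 0.3516 | 0.0351 |
| 4 | 0.0277 | 0.6353 | 0.0176 |
| 5 | 0.0055 | 0.8906 | 0.0049 |
| ≥ 6 | 0.0009 | 1 | 0.0009 |

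The sum is 0.0957. The same formula at p = 0.25 gives 0.811. A search over designs returns 1/13 and 5/34 as the optimum, so the plan's figures are right.

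**Step 2: add k Merkel patients.** Place them at random between the stages (hypergeometric: 34 patients, 13 in stage 1) with independent binomial responses. For k = 1, Merkel at 56% and the others at 10%, P(reject) is 0.1570 if that patient falls in stage 1 and 0.1340 if in stage 2:

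(13/34)(0.1570) + (21/34)(0.1340) = 0.0600 + 0.0827 = 0.143.

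| Others' true rate | Merkel rate | k = 0 | k = 1 | k = 2 |
|---|---|---|---|---|
| 10% | 25% | 0.096 | 0.111 | 0.128 |
| 10% | 56% | 0.096 | 0.143 | 0.203 |
| 7.5% | 25% | 0.031 | 0.040 | 0.050 |
| 7.5% | 56% | 0.031 | 0.056 | 0.094 |
| 5% | 56% | 0.005 | 0.012 | 0.027 |
| 25% | 56% | 0.811 | 0.838 | 0.861 |

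**Step 3: where the 0.10 line is crossed.** With Merkel at 56%, P(reject) passes 0.10 only if the others' true rate is above 8.9% (k = 1) or 7.7% (k = 2). With Merkel at 25% the values are 9.7% and 9.2%.

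**Step 4: is that a type I error?** With the others at 10% and Merkel at 56%, the pooled rate is (33 × 0.10 + 0.56)/34 = 11.4% for k = 1 and (32 × 0.10 + 2 × 0.56)/34 = 12.7% for k = 2. Both exceed the 10% null, so rejecting is not an error for the hypothesis in Section 12.

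**Step 5: effect on the estimate.** 6/34 = 17.6% (exact 95% CI 6.8% to 34.5%). Without one Merkel responder, 5/33 = 15.2% (5.1% to 31.9%).

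**The case for a change.** The best case for a change is that the eligibility text does not settle the matter. Section 3.2.1 itself calls Merkel neuroendocrine, the site list in 2.2 is open, and background prose is not a criterion. Criterion 5.2.12 rests on each investigator's opinion and may not be applied alike at every site. With the others at exactly 10%, one patient at 56% lifts the chance of a positive trial from 0.096 to 0.143. A line in Section 5 would close the question before anyone sees responses.

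Much of this is true. Merkel is not expressly excluded, and the figures are correct. But not expressly excluded is weaker than eligible: 5.1.1 asks for neuroendocrine carcinoma, and no section applies that term to Merkel. The thresholds in 5.1.1 are the Grade 3 cut-offs of Table 1, which grades gastroenteropancreatic tumours. That is not decisive, since 2.2 lists other sites too, but it ties the criterion to the disease described in 2.3 and 2.4.

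Entry would also need a patient treated first with platinum or temozolomide and never with a checkpoint inhibitor, in a disease where 3.2.1 reports pembrolizumab as widely accepted. Nothing in the documents suggests that such a patient was expected. Nor is the change quite free, because 16.11 requires IRB approval of an amendment before it is used.

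**Conclusion.** The concern does not call for a change. It is a missing detail about one rare site, and either answer to it would be acceptable. Pooling all non-pulmonary sites in one arm is the stated design, and the plan followed as written gives a sound test of its pooled hypothesis (alpha 0.096, power 0.811).

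Any harm needs three things together: a Merkel patient enrols despite 5.1.2 and 5.2.15, that patient responds, and the others' true rate lies close to 10%. If none enrols, nothing moves. With one or two enrolled and the others at 7.5% or below, the chance of a positive result stays below 0.10 even with Merkel at 56%. If the drug works in the others at 25%, power rises only from 0.811 to 0.838 or 0.861.

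What is left is a question of reading. A report of a 34-patient single-arm trial can describe responders by primary site without a prespecified rule, and 17.6% against 15.2% would hardly alter the interpretation. The sizes rest on assumed values for the number of Merkel patients (0 to 2) and their response rate (25% to 56%). Stating in Section 5 whether Merkel is in or out would be harmless as an optional clarification, but the primary analysis does not depend on it.
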